Clinical Research Abstract

Brief Title	Study on the Correlation Between Treg Immune Cells on the Muscle Content and Cognitive Functions of the Elderly
ID	ZDWY.LNBK.007
Sponsor	Fifth Affiliated Hospital, Sun Yat-Sen University
Research unit	Fifth Affiliated Hospital, Sun Yat-Sen University
Main researcher	[name]
Statistical unit and person in charge of statistics	Fifth Affiliated Hospital, Sun Yat-Sen University [name]
Research purposes	In order to explore the impact of the level of the elderly TREG immune cells and the effects of different fat distribution and muscle content, the impact of the level of TREG immune cells on cognitive functions is explored. The correlation between visceral fat content, subcutaneous fat content and cognitive function.
Sample size	100
Study Type	Observational
Selected standards for subjects	
Inclusion criteria:
 
1. 40-90 years old
 
Exclusion criteria:
 
previous diagnosis of dementia (including Alzheimer's disease, Lewy body dementia, Parkinson's disease, or other dementias) were excluded.

Research step	
1. Collect 2023-05-01 to 2024-12-31 Elderly patients who are consulting in our hospital at the same time improve the data measurement and TREG cell measurement data at the same time; 2. The level of TREG immune cells and different fat distribution and muscle content Impact; 3. The impact of the level of TREG immune cells on cognitive function; 4.

	Evaluate the effects of different fat distribution and muscle content on cognitive functions, evaluate the correlation between internal organs, subcutaneous fat content and cognitive functions; 5. Write the paper.
Terminal indicator	Cognitive function decline
Statistical Analysis	Use a linear regression model to analyze the level of the level of TREG immune cells, the effects of different fat distribution and muscle content; the impact of the level of TREG immune cells on the level of TREG immune cells is analyzed by the Mann-Whitney U test; the evaluation of different fat distribution and muscle content The impact on cognitive functions, evaluate the correlation between the content of visceral fat, subcutaneous fat content and cognitive functions. Statistical software includes SPSS27 and Graphpad Prism 8. Inspection level $\alpha = 0.05$.

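### The protocol fixes a two-group Mann-Whitney test for the Treg-cognition question in a single ungrouped sample of 100; if the variable it splits is a graded measure, an uncut analysis would use the same data with clearly more power

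*Protocol*

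**What the plan says.** The protocol is a one-table abstract. Four rows bear on this point.

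- **Statistical Analysis, first clause:** "Use a linear regression model to analyze the level of the level of TREG immune cells, the effects of different fat distribution and muscle content". Treg and body composition go into a linear regression.
- **Statistical Analysis, second clause:** the Treg analysis "is analyzed by the Mann-Whitney U test". In full, the clause reads "the impact of the level of TREG immune cells on the level of TREG immune cells is analyzed by the Mann-Whitney U test". As printed, Treg is both exposure and outcome. Research step 3 gives the matching aim as "The impact of the level of TREG immune cells on cognitive function", so cognition is the evident second variable.
- **Statistical Analysis, third clause:** "evaluate the correlation between the content of visceral fat, subcutaneous fat content and cognitive functions". No coefficient, model or scale is named.
- **Terminal indicator:** "Cognitive function decline".

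The design is observational, with 100 patients aged 40 to 90 and previously diagnosed dementia excluded. No arms, case and control groups or strata are defined. The significance level is 0.05, and sidedness is not stated.

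**The concern.** A Mann-Whitney test compares one variable between two groups, and this design does not supply two groups. To run the test, someone must create them, either by classing patients as declined or not declined, or by cutting Treg into high and low.

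On either route, the Treg-cognition aim seems to be handled more coarsely than its neighbours. If Treg is cut, it is binary here but goes into a linear regression one clause earlier. If cognition is cut, it is binary here, while the next clause speaks of a correlation with fat, which suggests (but does not state) a graded measure.

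What is at stake is power on the question in the study's title. The title describes a correlation study of Treg with muscle content and cognition, whereas the test named for cognition does not estimate a correlation. With only 100 patients, cutting a graded variable could turn an adequately powered analysis into an underpowered one.

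**Working it through.** **Plan's own figure.** The sample size of 100 cannot be reproduced, because the protocol states no effect size, standard deviation or power. What follows illustrates the cost of a split at that sample size.

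**Inputs from the protocol:** N = 100; alpha = 0.05.

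**Assumptions:** two-sided testing; Treg and a cognitive score bivariate normal; true correlation r from 0.20 to 0.40; splits of 50/50, 30/70 and 20/80. The model is symmetric in the two variables, so the results apply whichever one is cut.

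**Step 1: reference without a split (Fisher z).** Power = Φ(√(N − 3) · atanh(r) − 1.960).

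- At r = 0.30: √97 · atanh(0.30) = 9.849 × 0.3095 = 3.048, and Φ(3.048 − 1.960) = Φ(1.088) = 0.86.
- Correlation detectable with 80% power: tanh((1.960 + 0.842)/9.849) = tanh(0.2845) = 0.277, about 0.28.

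**Step 2: information kept after a split.** Cutting a normal variable so that a share p lies in one group multiplies its correlation with the other variable by φ(c)/√(p(1 − p)), where c is the cut point. The square of this factor is the relative efficiency.

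| Split | Factor | Relative efficiency | 100 patients worth about | Information lost |
|---|---|---|---|---|
| 50/50 | 0.3989/0.5 = 0.798 | 0.637 | 64 | 36% |
| 30/70 | 0.759 | 0.576 | 58 | 42% |
| 20/80 | 0.700 | 0.490 | 49 | 51% |

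**Step 3: power of the tests themselves.** Simulation with N = 100 and 8,000 runs per cell: Spearman on uncut data against Mann-Whitney after each split.

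| Assumed r | Spearman, no split | MW 50/50 | MW 30/70 | MW 20/80 |
|---|---|---|---|---|
| 0.20 | 0.48 | 0.34 | 0.32 | 0.27 |
| 0.25 | 0.66 | 0.49 | 0.46 | 0.40 |
| 0.28 | 0.76 | 0.59 | 0.55 | 0.48 |
| 0.30 | 0.83 | 0.66 | 0.60 | 0.53 |
| 0.40 | 0.98 | 0.89 | 0.86 | 0.80 |

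The simulation error is small: the standard error is at most √(0.25/8000) = 0.006.

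**Reading.** At the correlation that 100 patients can detect with about 80% power without a split (r about 0.28), the Mann-Whitney analysis has power of only 0.48 to 0.59. The uneven splits are relevant because patients with diagnosed dementia are excluded, so a group with decline may well be the minority. That is a plausibility argument; the protocol gives no proportion.

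**The case against.** The strongest counter-argument is that the clause is garbled and does not say what is split. A reader might infer that the cognitive endpoint is used in two forms, yes/no for Treg and continuous for fat. The documents do not support that. The Mann-Whitney clause does not mention cognition. If Treg is the variable cut, cognition can stay a score throughout. The fat clause says only that a correlation is evaluated, and the abstract uses that word loosely, so it cannot establish a continuous measure. The terminal indicator can also be read as a status, and comparing Treg between patients with and without decline is an ordinary use of the test. This objection stands, and it limits the point to the choice of test.

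Two further inferences also fail. One is that the Treg and fat results would be non-comparable. They would be on different effect scales, but a rank-biserial measure could stand beside a correlation, and no stated aim ranks Treg against fat. The other is that a single cut across ages 40 to 90 would mainly sort patients by age. Nothing in the protocol quantifies this, and an uncut raw score would carry age as well.

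It may also be said that the grouping and cut-off belong in an SAP, which is not shown. That is fair, and their absence is not the complaint. The test itself is fixed in the protocol, and a two-group test on graded data loses information wherever the cut is placed.

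Finally, the power figures rest on assumed correlations. They do, but the loss appears at every value tried.

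**Conclusion.** The point holds in a limited form. The protocol assigns a two-group test to what must be the Treg-cognition aim, in a single sample with no defined groups, although it regresses Treg in the clause before and correlates fat with cognition in the clause after.

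If the variable to be split is a graded measure, the cost is about 36% of the information at a median split and 51% at 20/80. Power at r = 0.30 falls from about 0.83 to between 0.66 and 0.53. Across assumed correlations of 0.20 to 0.40, the drop is from 0.48 to 0.34–0.27 at the low end and from 0.98 to 0.89–0.80 at the high end. These figures assume bivariate normality, two-sided testing and the stated splits.

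If decline is a genuine binary status that is not cut from a score, the power argument does not apply to it; the protocol defines no such status. This is a cheap improvement in method. It is not a demonstrated inconsistency in the endpoint.

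**What to change.** 1. Correct the misprinted clause so that it names Treg level and cognitive function.
2. Make the primary Treg-cognition analysis a rank correlation, or a regression, of the uncut cognitive score on the uncut Treg level. Regression is already in the plan for Treg and body composition.
3. Use the same cognitive score in the analyses of fat and muscle against cognition. The first clause, on Treg and body composition, has no cognitive endpoint and needs no change here.
4. If a Mann-Whitney comparison of Treg between patients with and without decline is wanted, keep it as secondary, and fix the grouping and cut-off before the data are analysed.

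The cost is a change of wording: same patients, measurements and software. The one downside is a result slightly less simple to display than two groups side by side.

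### Education is not named in data collection or analysis, although cognition is the only endpoint and its stated analyses carry no adjustment, so the cognition results could be confounded by education

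*Protocol*

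**What the plan says.** Everything relevant is in the protocol's Clinical Research Abstract.

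- **Study Type:** "Observational". Exposures are not randomised, and no eligibility rule concerns schooling.
- **Terminal indicator:** "Cognitive function decline", the only endpoint listed. No instrument, definition or number of assessments is given.
- **Research step 1:** the data collection is described only as "improve the data measurement and TREG cell measurement data at the same time". Education is not named; nor is any other background item.
- **Statistical Analysis, first clause:** "Use a linear regression model to analyze the level of the level of TREG immune cells" in relation to fat distribution and muscle content. No covariates are named.
- **Statistical Analysis, second clause:** this analysis "is analyzed by the Mann-Whitney U test". As printed, the clause has Treg level on both sides. The first clause serves step 2 and the third serves step 4, so the second evidently serves step 3, Treg level and cognition.
- **Statistical Analysis, third clause:** "evaluate the correlation between the content of visceral fat, subcutaneous fat content and cognitive functions". No specific method and no covariates are named.

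**The concern.** Performance on a cognitive test generally depends on schooling as well as on current brain function, and schooling may also go with lifestyle and hence body composition. This is subject knowledge used as an assumption; the protocol has no figures on it. If both links exist in this sample, education is a common cause of exposure and endpoint. A low score in a less-schooled patient could then be read as worse cognition linked to fat, muscle or Treg level. The aims are worded as effects on cognition, so this bears directly on what the study wants to conclude.

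The choice of covariates can normally be left to a SAP. Two features bring the point into the protocol. It already assigns a method to the evident Treg-cognition analysis, and that method compares two groups with no place for a covariate. It also decides what is collected, and a SAP can adjust only for an item that has been obtained. Regression is already in the plan, but it is not assigned to the cognitive endpoint.

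**Working it through.** **Inputs from the protocol.** n = 100 (Sample size row) and alpha = 0.05 (Statistical Analysis row). Sidedness is not stated; two-sided is assumed.

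**Inputs assumed.** Education-cognition correlation a = 0.3, 0.4, 0.5. Education-exposure correlation e = 0 to 0.4. For the power comparison, a true exposure-cognition effect of 0.25 on the standardised scale.

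**Step 0: the plan's own figure.** The sample size of 100 cannot be reproduced, because no effect size, SD or power is given. For orientation, the correlation detectable with n = 100 is tanh[(1.960 + z_power)/√97]. This is 0.277 at 80% power and 0.318 at 90%.

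**Step 1: false positives without adjustment.** With no true link, the correlation induced by education is r = a × e. By Fisher's z, the rejection rate is Φ(m − 1.960) + Φ(−m − 1.960), with m = atanh(r) × √97.

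Example, a = 0.4 and e = 0.3: r = 0.12; m = 0.1206 × 9.849 = 1.188; rate = Φ(−0.772) + Φ(−3.148) = 0.221.

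| e | a = 0.3 | a = 0.4 | a = 0.5 |
|---|---|---|---|
| 0 | 5.0% | 5.0% | 5.0% |
| 0.1 | 6.0% | 6.8% | 7.8% |
| 0.2 | 9.1% | 12.4% | 16.7% |
| 0.3 | 14.4% | 22.1% | 31.9% |
| 0.4 | 22.1% | 35.6% | 51.5% |

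**Step 2: power when education is unrelated to the exposure (e = 0).** The partial correlation is 0.25/√(1 − a²). Power uses √97 unadjusted and √96 with one covariate. The equivalent sample-size factor is 1/(1 − a²).

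| a | partial r | power unadjusted | power adjusted | sample-size factor |
|---|---|---|---|---|
| 0.3 | 0.262 | 71.1% | 74.8% | 1.10 |
| 0.4 | 0.273 | 71.1% | 78.3% | 1.19 |
| 0.5 | 0.289 | 71.1% | 82.9% | 1.33 |

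**Step 3: precision when education is related to the exposure.** With no exposure effect, the ratio of adjusted to unadjusted standard error is √[(1 − a²)/((1 − e²)(1 − (a·e)²))].

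| e | a = 0.3 | a = 0.4 | a = 0.5 |
|---|---|---|---|
| 0 | 0.954 | 0.917 | 0.866 |
| 0.3 | 1.004 | 0.968 | 0.918 |
| 0.4 | 1.048 | 1.013 | 0.964 |

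The precision gain is therefore largest where there is no confounding. It vanishes or reverses once e is about as large as a. The worst loss in this range is about 5% (1.048).

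**Limits.** Steps 1 to 3 concern a correlation or linear slope with education as the only covariate. They were not computed for the Mann-Whitney test, whose grouping the protocol does not define, nor with age added.

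**The case against.** The strongest case against is that this is a one-table abstract naming no covariate at all, not even age, and covariates are ordinary SAP material. That disposes of any complaint that education is merely missing from a covariate list. It does not dispose of the choice of an unadjustable test for what is evidently the Treg-cognition analysis, or of the value of naming an item at collection.

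Several stronger readings are tempting, and the document does not support them:

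- *Education will not be recorded.* The measurements in step 1 are unspecified. Read as a closed list, the step would also omit age and the cognitive test itself. Education is unnamed, not shown to be excluded.
- *The gap cannot be repaired later.* For patients already seen, the item may be obtainable from records or by phone.
- *Neither cognition analysis can adjust.* This holds for Mann-Whitney only. The fat-cognition clause names no method, and a partial correlation or regression would be compatible with it. What can be said is that no adjustment is stated.
- *Cognition is a raw score taken once.* This is an inference: no repeat assessment is described, but the endpoint is worded as a decline and is not defined. A score already corrected for schooling would meet part of the concern.
- *The results would be confounded and imprecise together.* Confounding needs e above zero, and the quoted power gains need e equal to zero. They are separate scenarios.

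It is also fair to object that a headline result adjusted for education alone would be poor in patients aged 40 to 90, because age confounding would remain. The fix takes this up.

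**Conclusion.** The point holds as a possibility that the stated analyses leave open, not as a demonstrated bias. Followed as written, the evident Treg-cognition test cannot account for education, and the fat-cognition analysis is not said to do so.

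The size depends entirely on assumed correlations. For education-cognition correlations of 0.3 to 0.5, the harm is nil if education is unrelated to the exposure and small at an education-exposure correlation of 0.1. It is material from about 0.2 upwards. The document offers nothing to place fat, muscle or Treg level on that scale, and the link to Treg is the least certain. The improvement is worth making because its cost is low against that range.

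**What to change.** 1. **Research step 1:** name years of education as a recorded item. For patients already seen, retrieve it from records or by phone.
2. **Statistical Analysis, for steps 3 and 4:** use a linear regression of the cognitive score on the Treg, fat or muscle variable, including years of education together with age. Report the adjusted coefficient with its 95% CI as the main result.
3. Keep the Mann-Whitney test and the unadjusted correlation as descriptive results. Correct the second clause so that it names cognition as the outcome.
4. State whether the cognitive score is already corrected for schooling, so that the adjusted coefficient can be interpreted.

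**Cost:** one question per patient, some retrieval work for those already seen, and a few degrees of freedom out of 100. Precision could fall by up to about 5% if education is strongly related to the exposure (standard-error ratio 1.048 at e = 0.4, a = 0.3). In that same case the unadjusted correlation would reject a true null 22.1% of the time.

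### Is a single 0.05 level across several unranked association tests an error in this protocol?

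*Protocol*

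**What the plan says.** The protocol is a short research abstract. It describes the design as "Study Type Observational" and gives "Sample size 100". Research purposes frames the aim as exploring how Treg level, body composition and cognition relate to one another.

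Three questions follow in Research step:

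- Step 2: Treg level with fat distribution and muscle content. The method, in Statistical Analysis, is "Use a linear regression model to analyze the level of the level of TREG immune cells, the effects of different fat distribution and muscle content".
- Step 3: "The impact of the level of TREG immune cells on cognitive function". The Mann-Whitney clause in Statistical Analysis appears to belong here, although as printed it names Treg level on both sides.
- Step 4: "Evaluate the effects of different fat distribution and muscle content on cognitive functions". Research purposes adds "The correlation between visceral fat content, subcutaneous fat content and cognitive function".

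One outcome is named: "Terminal indicator Cognitive function decline". One significance level closes the Statistical Analysis entry: "Inspection level $\alpha = 0.05". The protocol does not give the number of tests, does not rank the associations, and claims no control of error over the whole set.

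**The concern.** A reader who lists every pairing can reach seven tests: Treg level against visceral fat, subcutaneous fat and muscle (3), Treg level against cognition (1), and the same three body-composition measures against cognition (3). Each would be judged at 0.05 and none has priority. The named outcome does not settle the order, because four of the seven pairings involve cognition on equal terms.

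If that were a defect, any one result below 0.05 could be presented afterwards as the study's finding, and the chance of at least one such result with no true association anywhere would be well above 5%.

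**Working it through.** **Inputs.** The level of 0.05 is in Statistical Analysis. The three questions are steps 2 to 4 of Research step. The number of tests, k, is not in the protocol and has to be assumed. The protocol states no family-wise error rate, so there is no figure of its own to reproduce.

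**Family-wise rate under independence, all nulls true.** The formula is 1 − (1 − 0.05)^k.

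| k | How the count arises | Chance of at least one false positive |
|---|---|---|
| 3 | one test per research question | 1 − 0.95^3 = 14.3% |
| 4 | only the pairings with cognition | 1 − 0.95^4 = 18.5% |
| 7 | every measure tested separately (3 + 1 + 3) | 1 − 0.95^7 = 30.2% |

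For seven tests the upper bound under any dependence is 7 × 0.05 = 35%.

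**Effect of dependence.** The same body-composition measures recur and are plausibly correlated. A simulation with n = 100 and 20,000 runs set all associations under test to zero. It used six correlation tests (Treg and cognition, each against three body-composition measures) and one Mann-Whitney test of Treg by cognition group. The common correlation r among the three measures is an assumption:

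| r | Chance of at least one false positive in seven tests |
|---|---|
| 0 | 30.3% |
| 0.3 | 29.5% |
| 0.5 | 27.3% |
| 0.7 | 24.4% |
| 0.9 | 20.0% |

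**Is seven what the protocol fixes?** No. Visceral and subcutaneous fat are named separately only in relation to cognition. For Treg level the text speaks of fat distribution as a whole. The regression is described as one model, and a joint model with an overall test would use one test where the count of seven uses three. The text would also allow more than seven if several cognitive measures were used. Neither seven nor a minimum of seven can be read from it.

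**Does the sample size matter here?** No. For a valid test at a fixed level, the false-positive rate does not depend on n, so 100 participants neither cause nor worsen the multiplicity.

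**Is anything stated wrongly or contradicted?** The 0.05 level is a per-test level. Each valid test run at 0.05 has a 5% false-positive rate, as stated. A contradiction would need a passage that promises 5% over the whole set, calls the results confirmatory, or names a primary association and then treats others as equal to it. The protocol contains none of these.

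**The case for a change.** The strongest case for the concern is that choosing the association a study rests on is a design decision, not a technical detail to be deferred. This protocol has its own Statistical Analysis entry, sets a formal threshold there, and plans a paper as its last step. Naming cognitive decline as the outcome does not identify which exposure comes first. Even with r = 0.9 the family-wise rate for seven tests is 20.0%, four times 5%, and nothing says that the p-values will be descriptive.

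Part of this stands. The protocol ranks no association, and an isolated p-value just below 0.05 from such a set would be weak evidence. It does not follow that the plan is in error. Weak evidence is still some evidence, and even on the 30.2% figure the more probable outcome under the global null is no false positive at all (0.95^7 = 69.8%). The purpose is already worded as exploratory, so labelling the results exploratory would change little. Making an adjusted Treg-cognition association the primary one would be a preference: nothing in the text gives it that place, and the title puts muscle content and cognitive functions side by side. It would also replace what appears to be an unadjusted Mann-Whitney comparison with a different analysis.

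**Conclusion.** The concern does not hold. The calculation of 30.2% is correct for seven independent tests with every null true, but the protocol fixes neither that count nor that independence. Plausible readings give 14.3% for three independent tests and about 20% to 30% for seven with correlated measures. None of these figures conflicts with anything the protocol claims, because it sets a per-test level and promises no family-wise control.

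What is left is the absence of a hierarchy or adjustment rule from a short abstract of an observational, exploratory study. Such rules commonly sit in a statistical analysis plan, and statisticians reasonably differ on whether exploratory associations need them. The conclusion rests on reading the stated purpose as exploratory. It would change if a further document presented these associations as confirmatory or claimed a 5% error rate over all of them.
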